### **8.4. Study Assessments and Procedures**

#### **8.4.1. Physical Exams**

A complete physical examination will include, at a minimum, assessment of the Cardiovascular, Respiratory, Gastrointestinal and Neurological systems and skin. Height will also be measured and recorded at screening only and weight at screening and baseline only.

A brief physical examination will include, at a minimum, assessments of the skin, Respiratory, Cardiovascular system, and abdomen (liver and spleen).

#### **8.4.2. Vital Signs**

Vital signs will be measured in semi-supine position and will include temperature, systolic and diastolic blood pressure and pulse rate.

#### **8.4.3. Electrocardiogram (ECG)**

ECGs will be measured in semi-supine position.

Twelve-lead ECGs will be obtained during the study using an ECG machine that automatically calculates the heart rate and measures PR, QRS, QT, and QTcF intervals. Refer to Section 6.8.3 for QTcF criteria and additional QTcF readings that may be necessary.

#### **8.4.4. Clinical Safety Laboratory Assessments**

All protocol required laboratory assessments must be conducted in accordance with the SRM or Laboratory Manual, and Protocol Time and Events Tables (Section 8.1 and

Section 8.2). Laboratory requisition forms must be completed, and samples must be clearly labelled with the participant number, protocol number, site/center number, and visit date. Details for the preparation and shipment of samples will be provided by the laboratory and are detailed in the SRM or the laboratory manual. Reference ranges for all safety parameters will be provided to the site by the laboratory responsible for the assessments.

If additional non-protocol specified laboratory assessments are performed at the institution's local laboratory and result in a change in participant management or are considered clinically significant by the Investigator (e.g., SAE or AE or dose modification) the results must be recorded.

Hematology, clinical chemistry, urinalysis and additional parameters to be tested by central laboratory are listed below:

#### **Hematology**

Platelet Count	RBC Indices:	Automated WBC Differential:
Red Blood Cell (RBC)Count	Mean corpuscular volume (MCV)	Neutrophils
White Blood Cell (WBC) Count (absolute)	Mean corpuscular hemoglobin (MCH)	Lymphocytes
Reticulocyte Count	Mean corpuscular hemoglobin concentration (MCHC)	Monocytes
Hemoglobin		Eosinophils
Hematocrit		Basophils

#### **Clinical Chemistry**

Blood urea nitrogen (BUN)	Potassium	AST (SGOT)	Total and direct bilirubin
Creatinine	Chloride	ALT (SGPT)	Uric Acid
Glucose fasting [on Day 1 (baseline) and Week 7 only]	Total carbon dioxide (CO 2 )	Gamma glutamyltransferase (GGT)	Albumin
Sodium	Calcium (corrected)	Alkaline phosphatase (ALP)	Total Protein
Serum complement (CH50, C3)	Immunoglobulin M (IgM)	Immunoglobulin A (IgA)	
Immunoglobulin G (IgG)			

Since changes in ALP, total protein and albumin level can potentially unblind the investigator to which dose the participant has been randomized to; values for ALP, total protein, and albumin levels will be blinded to the site. An unblinded Medical Monitor will review this lab data on an ongoing basis for safety.

NOTE: Details of Liver Chemistry Stopping Criteria and Follow-Up Procedures are given in Appendix 2: Liver Safety Required Actions and Follow up Assessments.

#### **Routine Urinalysis**

Specific gravity, pH
glucose, protein, blood and ketones by dipstick
Microscopic examination (if blood or protein is abnormal)

#### **Other tests**

QuantiFERON®-TB Gold
Viral Serology [HIV1/HIV2, Hepatitis B (HBsAg), Hepatitis B (Core antibody), Hepatitis C (Hep C antibody)]
FSH (as needed for confirmation of postmenopausal status)
Pregnancy Tests: serum test at screening, Week 18, and early withdrawal and urine dipstick pre-dose at other timepoints. Positive urine tests should be confirmed with a serum test.

All laboratory tests with values that are considered clinically significantly abnormal during participation in the study should be repeated until the values return to normal or baseline. If such values do not return to normal within a period judged reasonable by the Principal Investigator, the etiology should be identified, if possible and the Sponsor notified.

#### **8.4.5. Pharmacokinetics**

Blood samples for PK analysis of RVT-1401 will be collected at the time points indicated in Section 8.1 and 8.2, Time and Events Tables. The actual date and time of each blood sample collection will be recorded.

Processing, storage and shipping procedures are provided in the SRM or lab manual.

Serum analysis will be performed under the control of the Sponsor. Concentrations of RVT-1401 will be determined in serum samples using the currently approved bioanalytical methodology. Raw data will be archived at the bioanalytical site.

#### **8.4.6. Anti-Drug Antibody (ADA) and Neutralizing Antibody (NAb)**

Blood samples for ADA and NAb analysis will be collected at the time points indicated in Section 8.1 and 8.2, Time and Events Tables. The actual date and time of each blood sample collection will be recorded.

Processing, storage and shipping procedures are provided in the SRM or lab manual.

ADA analysis will be performed under the control of the Sponsor. Anti-RVT-1401 antibody titers will be determined in serum samples using the currently approved bioanalytical methodology. Raw data will be archived at the bioanalytical site. If Anti-

RVT-1401 antibody titers are detected, they will be further characterized using a validated cell based Nab assay

#### **8.4.7. Pharmacodynamics**

Blood samples for PD analysis will be collected at times indicated in the Time and Events Tables (Section 8.1 and 8.2).

[figure not shown]
##### **Pharmacodynamic Markers**

Total IgG, and differentiation by class: IgG subclasses (IgG1, 2, 3, and 4)
--

Anti-AChR antibody levels
---------------------------

The actual date and time of each blood sample collection will be recorded. These samples may be used for the analysis of exploratory biomarkers. Samples will be collected, labelled, stored, and shipped as detailed in the SRM or lab manual.

#### **8.4.8. Exploratory Biomarkers**

## **8.5. Myasthenia Gravis Assessments**

### **8.5.1. Myasthenia Gravis Activities of Daily Living (MG-ADL)**

The MG-ADL is an 8-item, patient reported questionnaire that assesses MG symptoms and their effects on activities of daily living. The scale has been validated and shown to correlate with the QMG scale and newer MG outcome scales such as the MGC and MG-QOL15r [Wolfe, 1999, Muppudi, 2011].

Participants are asked to rate each item on a scale of 0-3. The MG-ADL score is calculated by totalling the rating for each of the 8 items. The scale takes approximately 2-3 min to complete and can be administered by the physician or trained clinic personnel or study coordinator. Details can be found within the SRM or study specific manual.

### **8.5.2. Quantitative Myasthenia Gravis Score (QMG)**

The QMG score was developed as a tool to assess MG disease severity and the pattern of deficits based on quantitative testing of affected muscle groups [Barohn, 1998]. The scale is comprised of 13 test items that are graded on a scale of 0-3. The total sum across all 13 items represents the QMG Score. The test takes approximately 30 minutes to perform and can be administered by a trained physician, research coordinator or clinical evaluator who has been trained for this study. Details can be found within the SRM or study specific manual.

### **8.5.3. Myasthenia Gravis Composite Score (MGC)**

The MGC was developed by selecting the best performing items from 3 commonly used MG-specific scales (QMG, MG manual muscle test, and MG-ADL) and is comprised of 10 functional domains: 3 ocular, 3 bulbar, 1 respiratory, 1 neck, and two limb items [Burns, 2008]. The scale measures symptoms and signs of MG in these domains incorporating both physician and patient-reported test items. The MGC takes approximately 5 min to complete and can be administered by a trained physician, research coordinator or clinical evaluator. Details can be found within the SRM or study specific manual.

### **8.5.4. Myasthenia Gravis Quality of Life 15 revised Score (MG-QOL 15r)**

The MG-QOL15r is a patient-reported scale designed to assess how their MG affects different aspects related to quality of life. There are 15 items that are graded on a scale of 0-2; the total across all 15 items represents the MG-QOL15r score. The survey takes approximately 2 minutes to complete by the participant. Details can be found within the SRM or study specific manual.

### **8.5.5. Satisfaction Questionnaire**

A brief survey asking participants for feedback on their experience with the SC injections during the course of the study will be completed at the end of the treatment period. The survey will take less than 2 min to complete by the participant.

## **9. DATA MANAGEMENT**

For this study, participant data will be entered into a Sponsor-approved electronic database and combined with data provided from other sources (e.g., safety laboratory, PK and PD vendor, etc.) in validated datasets then transmitted electronically to the Sponsor or designee.

Management of clinical data will be performed in accordance with applicable Sponsor approved standards and data cleaning procedures to ensure the integrity of the data, e.g., removing errors and inconsistencies in the data.

Adverse events and concomitant medications terms will be coded using Medical Dictionary for Regulatory Activities (MedDRA) and the World Health Organization Drug Dictionary Enhanced (WHO-DDE), respectively.

The Principal Investigator will retain original source documents and the Sponsor will receive eCRF-required data as electronic datasets. Participant initials will not be collected or transmitted to the Sponsor.

## **10. STATISTICAL CONSIDERATIONS AND DATA ANALYSES**

### **10.1. Sample Size Considerations**

The sample size for this study was not determined using statistical methods. The sample size was chosen based on clinical and recruitment considerations. However, the sample size of 14 active and 7 placebo participants will allow the study to show a 33% difference between either active arm and the placebo arm, assuming 90% power, equal standard deviations of 20 and an alpha of 0.05 using a two-sided z-test for the primary endpoint of percentage change from baseline in IgG at Week 7.

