### **Expected Treatment Effect**

[figure not shown]
The proposed dosing regimens are expected to provide a sustained total IgG reduction of approximately 75-80% and 65-70% for Regimen A and B respectively, following the fourth or fifth dose. It is expected that the nadir IgG reduction will occur by the 5th dose and be maintained following the sixth dose before rising back to baseline over the next 6 to 8 weeks. These assumptions are supported by preliminary PD results, shown in Figure 1, from the ongoing Phase 1 clinical study RVT-1401-1001 (Section 3.2.3). In healthy participants, 4 weekly SC injections of 680 mg of RVT-1401 produced an average total IgG percent reduction from baseline of 78%.

For participants that enter into the OLE, IgG levels will rise over the 2-week interval between week 6 and the start of OLE dosing at week 8. The IgG levels are expected to oscillate between decreasing and increasing over the next 3 doses, with trough IgG levels expected to rise by 15-25% above the nadir levels achieved during the treatment phase in the double-blind part of the study. Subjects who switch to 340 mg every 2 weeks from the placebo treatment are expected to achieve an IgG reduction of approximately 35-45% after the last OLE dose. Upon completion of OLE dosing, all subject IgG levels are expected to return to baseline over the next 6-8 weeks.

In study RVT-1401-1001, the inter-individual variability in IgG reduction and PK was larger in the 340 mg cohort vs. the 680 mg cohort; this difference can be explained by lower receptor occupancy in the 340 mg cohort throughout the dosing interval across all individuals. It is also noteworthy that, with both doses, the variability in exposure decreased with repeat dosing. This may indicate that full receptor occupancy is not lost within the dosing interval, and that with subsequent doses, more receptors are being occupied or remain occupied.

In the repeat dose 340 mg cohort, there were some individuals who did not achieve nadir IgG concentration until after the last dose, indicating they may have not reached steady state. In contrast, most subjects in the 680 mg cohort achieved nadir concentration prior to the last dose and maintained that response until after the last dose, indicating steady state response was achieved. Data from this study will be used to support dose selection in future studies.

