### 3.2.3.3. Pharmacodynamic

Following the administration of single SC doses of RVT-1401, total IgG reduction increased with increasing dose, with a maximum reduction of 47% observed after a fixed dose of 765 mg. The nadir for IgG reduction following single SC dosing occurred between days 8-15 in most individuals. IgG serum levels on average returned to within 90% of baseline by 43 days after drug administration. Albumin levels were also reduced from baseline when compared to placebo showing a similar dose related trend. The highest reduction occurring following the 765 mg SC dose (average ~14.5%) but were not considered to be clinically significant reductions as all patients remained within normal limits (3.5 g/dL to 5.5 g/dL) and levels recovered quickly, returning to baseline ~ 2 weeks after nadir.

The amount of IgG reduction has also been assessed following weekly SC administration of 340 and 680 mg of RVT-1401 or placebo for 4 weeks. There were 8 subjects with data out to day 35, that were included in a preliminary PD analysis for the 680 mg cohort and 7 subjects with data out to day 49 that were included in the analysis for the 340 mg cohort. One subject only received 2 doses of 340 mg prior to withdrawing due to personal reasons, their data was not included in the preliminary PD analysis. There were 4 placebo subjects with data out to day 35 pooled across two cohorts for analysis of PD endpoints. Figure 1 presents the mean IgG concentration-time profiles for both weekly SC administration of 340 mg and 680 mg doses. Figure 1 shows a reduction in serum IgG as a percent of pre-dose across both 340 mg and 680 mg cohorts. In contrast, the placebo group demonstrated minimal changes in serum IgG as a percent of pre-dose. The reduction in serum IgG was more rapid following the 680 mg SC compared vs 340 mg SC. The median IgG nadir concentration occurred prior to the last dose in the 680 mg cohort whereas for 340 mg, it occurred approximately 3 days after the last dose. The finding that the 680 mg cohort achieved nadir concentration following the 3rd dose and maintained serum IgG reduction after the 4th dose, indicates a maximum response has likely been achieved, and that higher doses or more frequent dosing would yield little additional benefit. This is consistent with data from other anti-FcRn agents in development that have observed a maximum percent reduction in serum IgG from baseline of ~ 75-80%.

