## 5.3. Treatment Arms and Duration

In the double-blind phase of the study, participants will be randomized 1:1:1 to one of the three blinded treatments illustrated in Figure 2.

In the OLE an additional 3 doses over a 6-week period (every 2 weeks) will be administered, illustrated in Figure 3.

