## 6. PARTICIPANT POPULATION

### 6.1. Type and Number of Participants

A sufficient number of participants will be enrolled to achieve approximately 21 evaluable participants. Enrollment is competitive.

In order to manage the total study enrollment, the Sponsor may suspend screening and/or enrolment at any site or study-wide at any time.

If participants prematurely discontinue the study, additional replacement participants may be enrolled at the discretion of the Sponsor.

Deviations from inclusion and exclusion criteria are not allowed because they can potentially jeopardize the scientific integrity of the study, regulatory acceptability or participant safety. Therefore, adherence to the criteria as specified in the protocol is essential.

To determine participant eligibility at screening, a single repeat of certain tests such as laboratory values, vital signs, or ECGs is allowed at the discretion of the Principal Investigator.

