### **10.3.1. Primary Endpoint for Efficacy**

The primary endpoint will be defined as the percentage change from Baseline in the IgG parameter at Week 7. The endpoint will be summarized using a 6-number summary including the sample size, mean, standard deviation, median, minimum and maximum values. Treatment group comparisons between the two active (separately) to the placebo arm will be performed using an Analysis of Covariance model with treatment and baseline value in the model. An alpha of 0.05 will be used to determine statistical significance.

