1.3. Sample Size and Power

Planned Sample Size and Power Statement	
A sufficient number of participants will be enrolled to achieve approximately 21 evaluable participants. The sample size for this study was not determined using statistical methods. The sample size was chosen based on clinical and recruitment considerations.
 
However, the sample size of 14 active and 7 placebo participants will allow the study to show a 33% difference between either active arm and the placebo arm, assuming 90% power, equal standard deviations of 20 and an alpha of 0.05 using a 2-sided z-test for the primary endpoint of percentage change from baseline in IgG at Week 7.

--	--

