8.4. The Population-level Summary

The population-level summary for this study includes the mean percent change in IgG of patients in the FAS who received RVT-1401 (combined) versus placebo followed by estimates of subjects receiving each dose. Response data from efficacy questionnaires will include mean changes, mean percent changes, and responder analysis as defined under variables of analysis.

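### The stated 90% power for a 33-point IgG difference between each active arm and placebo does not follow from the plan's own inputs, which give 87.0%; 90% power needs about 34.7 points.

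*Protocol*

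**What the plan says.** Protocol 10.1 first explains that the sample size rests on clinical and recruitment grounds and not on a statistical calculation. It then makes a quantitative claim, with placebo as the comparator: "the sample size of 14 active and 7 placebo participants will allow the study to show a 33% difference between either active arm". SAP 1.3 carries the same claim, "assuming 90% power, equal standard deviations of 20 and an alpha of 0.05 using a 2-sided z-test", for percentage change from baseline in IgG at Week 7.

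Three other places fix the group sizes and the comparison:

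- Protocol 5.3: "participants will be randomized 1:1:1 to one of the three blinded treatments".
- Protocol 6.1: "A sufficient number of participants will be enrolled to achieve approximately 21 evaluable participants". The 21 are therefore evaluable participants, and no dropout allowance enters the calculation.
- Protocol 10.3.1, on the primary endpoint: "Treatment group comparisons between the two active (separately) to the placebo arm will be performed using an Analysis of Covariance model".

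SAP 8.4 orders the comparisons differently. Its population-level summary takes patients "who received RVT-1401 (combined) versus placebo followed by estimates of subjects receiving each dose".

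**The concern.** The power sentence concerns a single active arm against placebo. Under equal allocation, 14 active participants are 7 on each dose, so that comparison is 7 against 7. A difference of 33 points with a standard deviation of 20 looked slightly too small for 90% power at that size, and the mention of 14 active participants raised the possibility that a pooled comparison had been computed and described as a per-arm one.

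What is at stake is the accuracy of a stated operating characteristic. A reader would take 90% as the power of each dose against placebo. The sentence stands in both documents and could be carried into later reports.

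**Working it through.** **Inputs**, all from the documents:

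- 7 participants per arm: 14 active and 7 placebo (Protocol 10.1, SAP 1.3), split 1:1:1 (Protocol 5.3).
- Standard deviation 20 in both groups, two-sided alpha 0.05, z-test, stated power 90%, stated difference 33 percentage points (Protocol 10.1, SAP 1.3).
- Normal quantiles: 1.9600 for two-sided 0.05 and 1.2816 for 90% power; their sum is 3.2415 before rounding.

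**Formulas**

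- SE = SD × √(1/n₁ + 1/n₂)
- Power at difference d = Φ(d/SE − 1.960). The opposite tail is negligible here.
- Difference detectable with 90% power = 3.2415 × SE

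**1. Attempt to reproduce the stated figure: one active arm against placebo, 7 against 7**

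- SE = 20 × √(1/7 + 1/7) = 10.690
- Power at 33 points = Φ(33/10.690 − 1.960) = Φ(1.127) = 0.870
- Detectable difference at 90% = 3.2415 × 10.690 = 34.65 points

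The stated figure is not reproduced. Power is 3.0 percentage points short, and the detectable difference is understated by 34.65 − 33 = 1.65 points. At 35 points, power is 90.6%.

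**2. Pooled active against placebo, 14 against 7**

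- SE = 20 × √(1/14 + 1/7) = 9.258
- Power at 33 points = Φ(33/9.258 − 1.960) = Φ(1.604) = 0.946
- Detectable difference at 90% = 3.2415 × 9.258 = 30.01 points

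This does not give 33 points at 90% either, and it is not the comparison the sentence describes.

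**3. Other possible explanations**

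| Variant | Power at 33 points | 90% detectable difference |
|---|---|---|
| 7 vs 7, two-sided 0.05 z-test (as stated) | 87.0% | 34.65 |
| 14 vs 7 pooled, two-sided 0.05 z-test | 94.6% | 30.0 |
| 7 vs 7, one-sided 0.05 z-test | 92.5% | 31.3 |
| 7 vs 7, two-sided 0.025 z-test | 80.1% | 37.7 |
| 7 vs 7, two-sided 0.05 t-test, 12 df | 80.9% | 37.8 |
| 8 vs 8, two-sided 0.05 z-test | 91.0% | 32.4 |

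Rounding of the 33 does not explain the gap: 32.5 to 33.5 points gives 86.0% to 88.0%. To have 90% power at 33 points with 7 per arm, the standard deviation would have to be 33/(3.2415 × √(2/7)) = 19.05. Keeping the standard deviation at 20 needs n = 2 × (20 × 3.2415/33)² = 7.72, that is 8 per arm.

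**4. Size of the gap against the expected effect**

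Protocol 3.2.2 expects a "sustained total IgG reduction of approximately 75-80% and 65-70% for Regimen A and B respectively". For Phase 1, Protocol 3.2.3.3 reports that "the placebo group demonstrated minimal changes in serum IgG as a percent of pre-dose". Taking placebo change as zero and the low end of 65 points, power for 7 against 7 is Φ(65/10.690 − 1.960) = 0.99998.

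**The case against.** The arithmetic is not in dispute. The case on the other side is about weight and remedy.

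- **The sentence is only illustrative.** The size was not chosen statistically, the target is approximate, and the gap amounts to one participant per arm. This stands, and it is why the point is minor. It does not make the sentence right: with the number fixed in advance, power and detectable difference are all that the sentence reports.
- **The SAP may intend the combined comparison.** SAP 8.4 puts combined active first, and the first hypothesis in SAP 9.2 refers to one dose or the other against placebo. If that test is the pooled one, 90% at 33 points understates its power of 94.6%. This stands as far as it goes, but SAP 1.3 still describes one arm against placebo.
- **The z-test is not the planned analysis.** Both documents plan ANCOVA with baseline adjustment. Estimating the standard deviation lowers power, to 80.9% with 12 degrees of freedom or 83.1% with 18. Baseline adjustment may raise it. The documents give no correlation between baseline and percentage change; if one assumes about 0.3, the residual standard deviation falls to 20 × √(1 − 0.3²) = 19.08, close to the 19.05 that would restore the claim on the z formula. So 87.0% describes the z-test named in the plan, not the ANCOVA.
- **A protocol change has a procedural cost.** Protocol 13.1.2 requires IRB or IEC approval for modifications. This stands and affects how the correction is best made.

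**Conclusion.** The stated power is wrong on its own inputs. For each active arm against placebo, with 7 per arm, a standard deviation of 20 and a two-sided 0.05 z-test, power at 33 points is 87.0%, and 90% power requires about 34.7 points. Neither the per-arm nor the pooled reading gives 33 points at 90%.

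The conclusion assumes exact 7:7:7 allocation, as the 14 and 7 imply, and covers only the z-test that the documents name. The error is minor. It does not threaten the IgG comparison, where the expected effect is roughly twice the detectable difference or more (65/34.65 = 1.9), and no design decision depends on it.

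**What to change.** Restate the sentence in Protocol 10.1 and SAP 1.3 along these lines: *With 7 participants per arm, a standard deviation of 20 and a two-sided 0.05 z-test, each active arm compared with placebo has 90% power for a difference of about 35 percentage points, and 87% power for 33 points.*

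Optionally, in SAP 1.3 only, add that combined active (14) against placebo (7) has 90% power for about 30 points, since SAP 8.4 lists that comparison first. It does not belong in Protocol 10.1, where the primary comparison is each arm separately.

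The drafting cost is one sentence in each document, with no change to sample size, design or analysis. Because a protocol change must go to the IRB or IEC, the protocol sentence can wait for the next amendment made for another reason. In the meantime, SAP 1.3 can be corrected and the difference noted in SAP 14.
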